	
 Percent achieving a minimal clinically important difference Adverse events reported via questionnaire (pain, epistaxis, etc.) Percentage willing to use again and recommend device to others Nasal obstruction symptom evaluation (NOSE) Score change

Overall Design:

This is a parallel, placebo-controlled multicenter randomized trial. The study population will consist of healthy volunteers with sinus headache/pain lacking objective evidence of chronic sinusitis. This will be a single-blinded study blinded to the participants. Because this study will involve minimal intervention from the investigators (i.e. participants will fill out surveys remotely), there will be minimal influence from the investigators and analysts end. Participants will be randomized to the treatment or the sham-placebo arm and the device they received (either device or sham), will be recorded in a secure database. Following screening, investigational intervention assignment will be performed by randomization in a 1:1, investigational device: sham ratio. Data will be collected and stored in an electronic data storage system.

Brief Summary:

The purpose of this study is to measure facial pain/pressure with a novel device using acoustic vibrations with oscillating expiratory pressure compared with a sham device in participants with sinus pain/headache lacking objective evidence of sinonasal inflammation.

Study details include:

- The study duration will be up to 12 months.
- The treatment duration will be up to 8 weeks.

- The visit frequency will be 0 visits. Participants will fill out questionnaires fielded via an electronic data capture system at 1 week, 2 weeks, 3 weeks, and 4 weeks of device use.

[figure not shown]
Number of Participants:

Approximately 120 participants will be screened to achieve 60 enrolled.

A maximum of 60 participants will be enrolled

Study Arms and Duration:

The total duration of study participation with screening, run-in (i.e., delivery of device), and device use is 11 weeks. Participants will use the investigational or sham device for 2 minutes, twice-daily for the entire 8-week study duration.

Data Monitoring/Other Committee:**1.2. Schema**

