7.1. Efficacy and/or Immunogenicity Assessments

Study outcomes will be assessed using the facial pain visual analogue scale (VAS)⁵, and Brief Pain Inventory-Short Form (BPI-SF)^{13,14}. The facial pain VAS score is a scale from 0-100 millimeters (mm) and asks patients to rate the severity of their facial pain over a previous one week recall period with higher scores indicating greater pain intensity. Additionally, a current VAS pain score and an immediate 5-minute post-use current VAS pain score will be assessed. A prior study looking at orofacial pain reported a minimal clinically important difference (MCID) of 1.2 for VAS pain. The BPI-SF assesses pain at its “worst”, “least”, “mean”, and “now” (current pain). In clinical trials, the items “worst” and “mean” have been each used singly to represent the pain severity. Worst and mean pain will be assessed over a previous one week recall period. BPI-SF also measures how much pain interferes (BPI interference) with seven daily activities including general activity, walking, work, mood, enjoyment of life, relations with others, and sleep. BPI pain interference is typically scored as the mean of the seven interference items. All items are rated on a 0-10 scale with 0 representing no pain/no interference and 10 representing pain as bad as you can imagine/interferes completely. A distribution-based approach using one-half the SD will be used to determine MCID values for BPI-SF, as there is a paucity of research assessing the MCIDs for these pain measures for facial pain/headache. Planned timepoints for all efficacy assessments are provided in the SoA.

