8.3.1.1. Main Analytical Approach

Statistical analysis will be conducted using SPSS version 25 (Armonk, NY: IBM Corp). Descriptive statistics such as means, range, standard deviations, frequencies, and percentages will be generated in order to present the baseline characteristics of both treatment arms. All continuous variables will be tested for normal distribution as determined by the Shapiro-Wilk test. To evaluate differences in outcome metrics between treatment arms (SinuSonic group vs sham control), paired t-tests will be used for normally distributed variables. Wilcoxon signed rank tests were used for non-normally distributed or ordinal variables. For all tests, a value of $p \leq 0.05$ will be considered statistically significant. The mean change between baseline and follow-up variables of interest will be calculated and measured against previously reported MCID thresholds when available or by using one-half of the baseline SD if not previously reported. Any missing data points will be excluded from analysis and handled similarly across all data points.

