8.4. Sample Size Determination

Approximately 60 participants will be enrolled. The sample size calculation is based on the primary efficacy estimand and its endpoint.

It is assumed that the proportion of participants achieving response for facial pain VAS is [30)% in the placebo intervention arm and [70)% in the arm receiving [intervention SinuSonic]. Using the normal approximation method for a 2-sided statistical test as described in Section 9.3.2, a study with an overall sample size of N = 60] participants will have over 90% power to detect a treatment difference between the two investigational interventions at a type-1 error level of 5%.

9. Supporting Documentation and Operational Considerations

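### The percent-achieving-MCID endpoint and the response rate behind the sample size have no responder definition or between-arm analysis, and the mean-versus-MCID step does not supply one

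*Combined protocol and SAP*

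**What the plan says.** The combined protocol and SAP treats the MCID and response in four places.

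- **Endpoint.** Section 1.1, Table 1 lists "Percent achieving a minimal clinically important difference". The table is broken in the text available, so its row is uncertain. Section 3 does not list this endpoint, and Section 8.1 has no hypothesis for it.
- **Threshold.** Section 7.1 cites a prior orofacial pain study that "reported a minimal clinically important difference (MCID) of 1.2 for VAS pain", without naming the scale. The VAS is 0-10 in Table 1 and 0-100 mm in Section 7.1. For BPI-SF, Section 7.1 uses half the SD.
- **Sample size.** Section 8.4 rests on "the proportion of participants achieving response for facial pain VAS", taken as 30% on sham and 70% on SinuSonic, with N = 60 and over 90% power. It names a two-sided normal-approximation method and refers to Section 9.3.2 for the test. The document has no Section 9.3.2.
- **Analysis.** Sections 8.3.1 and 8.3.1.1 carry the same paragraph. Its MCID rule is "The mean change between baseline and follow-up variables of interest will be calculated and measured against previously reported MCID thresholds when available". Where there is no published value, the fallback threshold is half the baseline SD. Separately, the paragraph plans an arm comparison: "To evaluate differences in outcome metrics between treatment arms (SinuSonic group vs sham control), paired t-tests will be used for normally distributed variables", with signed rank tests otherwise. Percentages appear there only in this form: "frequencies, and percentages will be generated in order to present the baseline characteristics of both treatment arms".

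**The concern.** Table 1 uses the MCID as a threshold that each participant does or does not reach, and the pilot summary in Section 1.1 does the same (about 70% of patients achieving it). The analysis rule instead sets a group mean of before-to-after change against that threshold. This raises two problems.

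First, the quantity that drives the sample size never reaches the analysis section. No responder is defined there, and no estimate or test of a difference in proportions is given.

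Second, the rule that is given contains no sham contrast. Sham response, or regression to the mean after the VAS entry cut-off of 5 in Section 5.1, can carry a mean past the threshold in either arm. A statement that the mean change exceeded the MCID would then carry no information about the device.

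**Working it through.** **1. The plan's own power figure.** Inputs from Section 8.4: p = 0.30 and 0.70, two-sided alpha 0.05, N = 60 at 1:1, so 30 per arm.

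- SE under the alternative: sqrt(2 × 0.21/30) = 0.1183.
- SE under the null (pooled p = 0.5): sqrt(2 × 0.25/30) = 0.1291.
- Unpooled: Phi(0.40/0.1183 − 1.96) = Phi(1.42) = 92.2%.
- Pooled: Phi((0.40 − 1.96 × 0.1291)/0.1183) = Phi(1.24) = 89.3%.
- Fisher's exact test, by summing over all binomial outcomes: 83.8%.

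The stated figure of over 90% is reproduced by the unpooled form, and to within a point by the pooled form. It is the power of a two-proportion comparison, which the analysis section does not specify.

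**2. What the mean-versus-MCID step can show.** The documents do not give the SD of change. Section 1.1 gives pilot VAS SDs of 15.7 mm (baseline) and 21.7 mm (4 weeks). With an assumed correlation r:

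SD of change = sqrt(15.7² + 21.7² − 2r × 15.7 × 21.7)

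- r = 0: sqrt(717.4) = 26.8 mm.
- r = 0.7: sqrt(717.4 − 477.0) = 15.5 mm.

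Take the threshold as 12 mm, which assumes that the 1.2 refers to a 0-10 scale. Let both arms have the same true mean improvement m, so the device effect is zero. With 30 per arm and a normal approximation:

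P(active mean ≥ 12) = Phi((m − 12)/(SD/sqrt(30)))

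| m, both arms (assumed) | SD 26.8 mm | SD 15.5 mm |
|---|---|---|
| 12 mm | 50% | 50% |
| 15 mm | 73% | 85.5% |
| 20 mm | 94.9% | 99.8% |
| 25 mm | 99.6% | above 99.9% |

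For m = 20 mm: 8/(26.8/5.48) = 1.64 gives 94.9%, and 8/(15.5/5.48) = 2.83 gives 99.8%. If the 1.2 were on the 0-100 mm scale, the threshold would be passed still more easily: at m = 20 mm and SD 26.8 mm, (20 − 1.2)/4.89 = 3.84, above 99.9%.

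**3. What a per-participant comparison would show in the same case.** With normally distributed changes and m = 20 mm, the proportion reaching 12 mm is Phi(8/26.8) = 61.7% or Phi(8/15.5) = 69.7%, the same in both arms. The expected risk difference is zero, which is the correct answer when the device does nothing.

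**The case against.** The strongest reply is that the trial is not left without a sham comparison. The paragraph holding the MCID sentence also plans a SinuSonic-versus-sham comparison of outcome metrics. Section 8.1 makes superiority over sham the objective, and Section 3 sets the summary as the difference in mean changes. All of that stands. A reader might infer that the plan lets the device be declared effective on its own before-to-after change. The documents do not support that: the MCID sentence states no decision rule, and nothing lets it replace the between-arm contrast. Whether paired tests suit two independent arms is a separate matter.

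A reader might also infer that each arm's mean is to be held against the MCID as the verdict on clinical relevance. The sentence does not say whose mean; it could even be a pooled change. It may be loose wording for a responder analysis. No reading supplies a sham contrast, a responder definition or a test, so the gap remains.

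It is also tempting to say that about 30% of pilot patients missed a 12 mm VAS threshold although the mean change was 59.6 − 34.6 = 25.0 mm. The pilot's 70% is reported across all pain metrics, and no pilot VAS threshold is given, so that figure cannot be used.

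Finally, Section 8.4 does mention a method for proportions, and Section 8.3.2 defers further detail to the SAP. But the section that 8.4 cites is absent, and the combined document holds no further analysis text.

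**Conclusion.** The concern holds in a limited form. The percent-achieving-MCID endpoint and the VAS response rate behind N = 60 have no responder definition and no between-arm analysis in Section 8.3. The mean-versus-MCID step cannot fill that gap because it has no sham contrast. With no device effect and an assumed 20 mm improvement in both arms, the active mean would reach 12 mm about 95% to 99.8% of the time.

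That range rests on pilot SDs at 4 weeks, an assumed r of 0 to 0.7, 30 analysed per arm and a 0-10 reading of the 1.2. The size of any sham improvement is an assumption, not a figure from the plan. Treating response in Section 8.4 as reaching the MCID is likewise an inference. The planned between-arm comparison of outcome metrics is not affected by this point.

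**What to change.** - Replace the mean-versus-MCID sentence in Sections 8.3.1 and 8.3.1.1, or label it descriptive only.
- Classify each participant at week 8 by own change from baseline against a stated threshold. For VAS, confirm the scale of the 1.2; it equals 12 mm only if it refers to 0-10. For BPI-SF, use half the baseline SD.
- State how participants with missing week-8 values are classified. The present text only excludes missing data points.
- Compare the proportions between arms as a risk difference with a 95% CI, using a two-proportion test consistent with Section 8.4's normal approximation (89.3% power pooled, 92.2% unpooled at 30 per arm). If Fisher's exact test is chosen, restate the power as about 84%.
- Report the between-arm difference in mean change, with its CI, beside the responder result.

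The cost is revised wording and one table. No new data are needed.

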8.3.2. Other Analyses

Subgroup analyses of the primary endpoint and confirmatory secondary endpoints will be made to assess consistency of the investigational intervention effect across the following subgroups:

- Age group: < 65 vs ≥ 65 years
- Sex: female vs male
- Race: white vs black vs. other

If the number of participants is too small (less than [10%]) within a subgroup, then the subgroup categories may be redefined prior to unblinding the study. The analyses will be conducted using a test for heterogeneity and results will be presented on forest plots presenting the estimated study arm difference and 95% confidence intervals. Further details on the statistical analysis will be provided in the SAP.

8.4. Sample Size Determination

Approximately 60 participants will be enrolled. The sample size calculation is based on the primary efficacy estimand and its endpoint.

It is assumed that the proportion of participants achieving response for facial pain VAS is [30)% in the placebo intervention arm and [70)% in the arm receiving [intervention SinuSonic]. Using the normal approximation method for a 2-sided statistical test as described in Section 9.3.2, a study with an overall sample size of N = 60] participants will have over 90% power to detect a treatment difference between the two investigational interventions at a type-1 error level of 5%.

9. Supporting Documentation and Operational Considerations

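### The over-90% power in Section 8.4 holds only under one variance formula and with at least 56 of 60 participants evaluable at Week 8, yet no attrition is allowed for

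*Combined protocol and SAP*

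**What the plan says.** Section 8.4 bases the sample size on response in facial pain VAS, with assumed proportions printed as "30)% in the placebo intervention arm and [70)% in the arm receiving [intervention SinuSonic" (the stray brackets are in the source). The calculation is described as "Using the normal approximation method for a 2-sided statistical test", with a pointer to Section 9.3.2, and the conclusion is that 60 "participants will have over 90% power to detect a treatment difference between the two investigational interventions at a type-1 error level of 5"%. Neither the variance formula nor the test is named. The protocol has no Section 9.3.2. The similarly numbered 8.3.2 covers subgroup analyses.

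The Synopsis (1.1, Number of Participants) states: "A maximum of 60 participants will be enrolled". Section 8.4 itself says approximately 60. Sections 8.3.1 and 8.3.1.1 both state: "Any missing data points will be excluded from analysis and handled similarly across all data points".

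Section 6.9 asks that a participant who permanently stops the device stay under evaluation for one week where possible. Section 6.10 ends study participation at withdrawal, and Section 6.11 covers loss to follow-up. No section gives an expected attrition rate or an inflation of the sample size.

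**The concern.** The power statement uses the number enrolled as if it were the number analysed. The cap leaves no room to enrol extra participants against losses, and dropping missing values turns each missing Week 8 record directly into a smaller sample. Someone who stops the device in, say, Week 3 and is followed for one more week has no Week 8 value. The margin above 90% is thin to begin with and depends on a formula that the plan does not name.

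The sponsor and the ethics board will use this figure to judge how informative a null result would be. If true power is in the low or middle eighties, a null result is weaker evidence against the assumed effect than Section 8.4 suggests.

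**Working it through.** **Inputs.** p1 = 0.30, p2 = 0.70, two-sided alpha 0.05 (z = 1.96), total 60 (all from 8.4); 1:1 allocation (4.1), so n = 30 per arm. The difference is 0.40. The unpooled variance term is 0.3 × 0.7 + 0.7 × 0.3 = 0.42. The pooled term is 2 × 0.5 × 0.5 = 0.50.

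**Reproducing the stated figure at 30 per arm.**
- Unpooled: Φ(0.40/√(0.42/30) − 1.96) = Φ(3.381 − 1.960) = 92.2%. This agrees with over 90%.
- Pooled: Φ((0.40 − 1.96 × √(0.50/30))/√(0.42/30)) = Φ(0.1470/0.1183) = 89.3%.
- Exact power of the uncorrected chi-square test, by enumerating both binomial distributions: 89.6%.
- Arcsine approximation: 89.0%.

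Of these, only the unpooled form exceeds 90%.

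**Evaluable number needed for 90%.**
- Unpooled: n = 0.42 × (1.960 + 1.282)²/0.40² = 27.6, so 28 per arm, 56 in total. Power is 90.4% at 28 + 28, 89.9% at 28 + 27 and 89.4% at 27 + 27. At most 4 of 60 (6.7%) can be lost.
- Pooled: 31 per arm, 62 in total, which is already above the cap.

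**Power with enrolment held at 60.** The loss rates are assumptions.

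| Loss | Evaluable | Unpooled | Pooled | Exact chi-square |
|---|---|---|---|---|
| 0% | 60 | 92.2% | 89.3% | 89.6% |
| 10% | 54 | 89.4% | 85.7% | 84.0% |
| 20% | 48 | 85.6% | 81.2% | 83.6% |

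The exact column does not fall smoothly because the test is discrete. At 5% loss (57 evaluable) the two normal approximations give 90.9% and 87.6%.

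**What 90% would take if losses were covered by enrolment.** Unpooled: 56/0.9 = 62.2, so 63, and 56/0.8 = 70. Pooled: 62/0.9 = 68.9, so 69, and 62/0.8 = 77.5, so 78. All four exceed the cap.

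**The comparison in the primary estimand.** Section 3 summarises the effect as a difference in mean change, not in responder proportions. If changes are normal with a common SD, 30% against 70% implies a standardised difference of z(0.70) − z(0.30) = 2 × 0.524 = 1.05. A two-sample t-test then has power of 97.9% at 30 per arm, 96.6% at 27 and 94.5% at 24.

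**The case against.** The best defence is that nothing in 8.4 is miscalculated: the figure follows from a standard formula of the kind the section names. The sections on withdrawal and loss are routine contingency text, and 6.9 calls discontinuation rare. If no more than 4 of 60 are lost, the unpooled claim stands. All of that is right. It makes the shortfall conditional, but it does not supply the missing attrition assumption or say which formula was used.

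It can also be said that Section 8.2 analyses efficacy in all randomised participants, so 60 would be counted. The rule excluding missing values overrides that in practice. Counting missing participants as non-responders would not rescue the figure: with loss unrelated to response, the rates become 27% against 63% at 10% loss and 24% against 56% at 20%, and pooled power at 30 per arm is 81.7% and 72.7%.

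A reader might infer several stronger points that the documents do not support:
- That all 60 must be evaluable. The unpooled formula needs 56, and under the pooled formula even 60 are too few, so 60 is not the threshold either way.
- That the shortfall applies to any endpoint. Under the normal, common-SD assumption, the comparison of mean change keeps 94.5% power at 24 per arm.
- That the chance of missing the assumed effect roughly doubles or more. Against a 10% benchmark, 10 to 20% loss gives 10.6 to 14.4% unpooled (1.1 to 1.4 times) and 14.3 to 18.8% pooled (1.4 to 1.9 times). About 2.5 times is reached only with Fisher's exact test (75.0% power at 24 per arm), which the plan names nowhere.
- That lost participants may not be replaced. The plan sets a maximum but is silent on replacement.

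**Conclusion.** The point holds in conditional form, for the responder comparison that 8.4 powers. The stated power rests on the unpooled formula and on losing no more than 4 of 60 participants. Under pooled variance or the exact chi-square test it is missed by less than one percentage point before anyone is lost. With an assumed 10 to 20% loss it is about 86 to 89% unpooled or 81 to 86% pooled. Both normal approximations stay above 80% over that range, so the defect is moderate: the statement should be corrected, but the design does not fail because of it.

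The loss rates are assumed. The t-test figures rest on a distributional assumption that the protocol does not make. That the powered endpoint is not the primary one is a separate and larger issue, and resolving it would replace the calculation discussed here.

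**What to change.** Rewrite the paragraph in 8.4, keeping enrolment at 60:
- State the assumed attrition and the resulting evaluable number, for example 48 to 54 for 10 to 20% loss.
- Name the test and the variance formula, and make the power calculation agree with them.
- Replace the over-90% statement with the power at the evaluable number (about 81 to 86% if pooled variance is chosen, about 86 to 89% if unpooled).
- Replace the reference to Section 9.3.2 with one to the section that describes the test.

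If the sample size is re-based on the difference in mean change, give the power for that comparison at the evaluable number instead, with its assumed difference and SD.

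The cost is one paragraph and, if the responder calculation is kept, a less favourable figure. No additional participants are needed.

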9.1.1. Regulatory and Ethical Considerations

- This study will be conducted in accordance with the protocol and with the following:
 - Consensus ethical principles derived from international guidelines including the Declaration of Helsinki and Council for International Organizations of Medical Sciences (CIOMS) international ethical guidelines
 - Applicable ICH Good Clinical Practice (GCP) guidelines
 - Applicable laws and regulations
- The protocol, protocol amendments, ICF, investigator's brochure, IDFU, and other relevant documents (e.g., advertisements) must be submitted to an IRB/IEC by the investigator and reviewed and approved by the IRB/IEC before the study is initiated.
- Any amendments to the protocol will require IRB/IEC approval before implementation of changes made to the study design, except for changes necessary to eliminate an immediate hazard to study participants.
- Protocols and any substantial amendments to the protocol will require health authority approval prior to initiation except for changes necessary to eliminate an immediate hazard to study participants.
- The investigator will be responsible for the following, as applicable:
 - Providing written summaries of the status of the study to the IRB/IEC annually or more frequently in accordance with the requirements, policies, and procedures established by the IRB/IEC
 - Notifying the IRB/IEC of SAEs or other significant safety findings as required by IRB/IEC procedures
 - Providing oversight of the conduct of the study at the site and adherence to requirements of 21 CFR, ICH guidelines, the IRB/IEC, European regulation 536/2014 for clinical studies, European Medical Device Regulation 2017/745 for clinical device research, and all other applicable local regulations

Investigators and sub investigators will provide the sponsor with sufficient, accurate financial information as requested to allow the sponsor to submit complete and accurate financial certification or disclosure statements to the appropriate regulatory authorities. Investigators are responsible for providing information on financial interests during the course of the study and for 1 year after completion of the study.

